7. ADVERS E EVENT REPORTING REQUIREMENTS

Adverse events will be assessed and will be graded according to the NCI CTC v4.0. CTC v4.0 can be accessed on the Internet at <http://ctep.info.nih.gov>. All Grade 4 toxicities should be reported (using a MedWatch form) to the Principal Investigator, the Data Safety and Toxicity Committee and the IRB.

Expedited Reporting Requirements:

- A. The Study Chair and Site Principal Investigator must be notified within 24 hours of learning of any serious adverse events, regardless of attribution, occurring during the study or within 30 days of the last administration of the study drug.
- B. The UCSD Human Research Protections Program (HRPP) and the Data and Safety Toxicity Committee must be notified within 10 business days of “any unanticipated problems involving risk to subjects or others” (UPR).

The following events meet the definition of UPR:

1. Any serious event (injuries, side effects, deaths or other problems), which in the opinion of the Principal Investigator was unanticipated, involved risk to subjects or others, and was possibly related to the research procedures.
2. Any serious accidental or unintentional change to the IRB-approved protocol that alters the level of risk.
3. Any deviation from the protocol taken without prior IRB review to eliminate apparent immediate hazard to a research subject.
4. Any new information (e.g., publication, safety monitoring report, updated sponsor safety report), interim result or other finding that indicates an unexpected change to the risk/benefit ratio for the research.
5. Any breach in confidentiality that may involve risk to the subject or others.
6. Any complaint of a subject that indicates an unanticipated risk or that cannot be resolved by the Principal Investigator.

The **Institutional Review Board (IRB) of each site** must be notified by the site principal investigator according to their local policies.

The **FDA** must be notified according to the following timelines:

- within 7 calendar days of any unexpected fatal or life-threatening adverse event with possible relationship to study drug, and
- within 15 calendar days of any event that is considered: 1) serious, 2) unexpected, and 3) at least possibly related to study participation.

Routine Reporting Requirements

- A.** The **UCSD HRPP** must be notified of any adverse events that are not unanticipated problems involving risk to subjects or others (non-UPRs) at the time of the annual Continuing Review.
- B.** The **IRB of each site** must be notified by the site principal investigator according to their local policies.

The **FDA** must be notified of all non-serious adverse events annually at the time of the annual report.

For this protocol, hospital admission for the nephrectomy procedure will not be considered an SAE. Complications secondary to surgery delaying discharge will be considered an SAE.

Patients will be followed for toxicity (of drug and/or surgical procedure) until 30 days after the date of partial nephrectomy, unless there is drug-related toxicity in which case patients will be followed until toxicity resolution to grade 1 or less.

Reporting to Pfizer:

Any serious adverse events which occur during the clinical study or within 5 days of receiving the last dose of study medication, whether or not related to the study drug, must be reported by the investigator. In addition, any SAEs which occur as a result of protocol specific diagnostic procedures or interventions must also be reported.

All serious adverse events must be reported by facsimile within 24 hours to Pfizer. MDC - Oncology [contact].

For medical emergencies contact: Site PI

The SAE report should comprise a full written summary, detailing relevant aspects of the adverse events in question. Where applicable, information from relevant hospital case records and autopsy reports should be included. Follow-up information should be forwarded to Pfizer within 24 hours.

SAEs brought to the attention of the investigator at any time after cessation of pazopanib and considered by the investigator to be related or possibly related to pazopanib must be reported to GSK if and when they occur. Additionally, in order to fulfill international reporting obligations, SAEs that are related to study participation (e.g., procedures, invasive tests, change from existing therapy) or are related to a concurrent medication will be collected and recorded from the time the subject consents to participate in the study until he/she is off study.

Data Safety Monitoring Plan

This protocol will adhere to the policies of the Cancer Center Data and Safety Monitoring Plan, version 2 guidelines in accordance with NCI regulations. The Data and Safety Toxicity Committee will compose of the principal investigator and the sub-investigators participating in this research study. The committee will convene electronically and by phone on a monthly basis to review safety and toxicity information.

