4.1 Axitinib Administration

Pfizer will supply Axitinib and it will be shipped in labeled boxes, with unlabeled bottles inside. The pharmacy must have labeling capabilities and fax all requests to Pfizer using the Drug Supply Request Form. Contact information is as follows:

[name], CCRC
[contact]
[contact]
[contact]

Pfizer will be provided with detailed mailing instructions, address/location of Pharmacy, Pharmacist in charge, or anything else that may be helpful for shipping.

Treatment will be administered on an outpatient basis. Axitinib will be initially dosed at 5 mg po BID with or without food. Patients tolerating axitinib at week 4 with no more than grade 2 toxicity and blood pressure controlled to $< 140/90$ mmHg (medication permitted) will have axitinib dose increased to 7mg BID. Axitinib will be dosed for a total of 8-10 weeks.

Swallow axitinib whole with a glass of water; do not split, crush, or chew. If the patient vomits

or misses a dose, an additional dose should not be taken; the next prescribed dose should be taken at the usual time

No investigational or commercial agents or therapies other than axitinib may be administered with the intent to treat the patient's malignancy.

Axitinib should be held for 1 day prior to surgery.

No axitinib will be administered after nephrectomy for any patient.

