5. STUDY CALENDAR

	≤ 4 weeks prior to dosing	Baseline	Day 14 (± 3 days)		Day 28 (± 3 days)	End of Cycle (Day 58 ± 3 days)	End of Treatment ¹
Informed Consent	X						
Vital Signs/ECOG	X	X	X		X	X	X
History / Physical	X	X	X		X	X	X
Hematology ²	X	X*	X		X	X	X
Chemistries ³	X	X*	X		X	X	X
Coagulation ⁴	X					X	
Pregnancy Test ⁵	X						
Urinalysis ⁶	X				X	X	X
Drug Related AE's		X	X		X	X	X
TSH, T3, T4	X					As clinically indicated	X
Axitinib**		X-----X					
Tumor Imaging ⁷	X				X	X	

* Cycle 1, day 1 labs need not be repeated if done within 14 days. ;** Nephrectomy will be performed ≥ 1 days after the last dose of Axitinib

Footnotes for Schedule of Events

1. End of Treatment/Withdrawal: These assessments will occur at least 30 days after nephrectomy date.
2. Hematology: CBC with differential, platelets
3. Blood Chemistry: Albumin, total bilirubin, bicarbonate, BUN, calcium, chloride, creatinine, glucose, magnesium, phosphorus, potassium, SGOT [AST], SGPT [ALT], sodium, ALP, LDH (baseline only).
4. Coagulation: PT/INR and PTT
5. Pregnancy Test: Serum or urine test must be performed for all women of childbearing potential.
6. Urinalysis: with 24 hour urine to ensure protein < 2 grams for anyone with 2+ or greater protein on urinalysis.
7. Tumor Imaging: CT or MRI scan of the chest, abdomen and pelvis (with IV contrast, if possible) to be performed to assess disease status at screening, prior to nephrectomy and whenever disease progression is suspected. CT or MRI scan of the chest is optional at day 28 based on symptoms or pre-enrollment findings. CNS and bone imaging needed only if clinical signs/symptoms are suggestive. Follow up imaging after nephrectomy at the discretion of the treating MD and not part of this protocol.

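### Section 7 never defines when the study ends for SAE reporting, and its 5-day, 30-day and post-surgery limits do not line up

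*Protocol*

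**What the plan says.** Section 7 of the protocol contains several time limits for safety events.

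- **Study Chair and Site PI** (Expedited Reporting Requirements, item A): SAEs of any attribution, "occurring during the study or within 30 days of the last administration of the study drug".
- **Pfizer** (in the subsection on reports to the supplier): "Any serious adverse events which occur during the clinical study or within 5 days of receiving the last dose of study medication". Attribution plays no part in this rule. The protocol's next sentence adds, with no day limit, that "any SAEs which occur as a result of protocol specific diagnostic procedures or interventions must also be reported".
- **Toxicity follow-up** (Routine Reporting Requirements): "Patients will be followed for toxicity (of drug and/or surgical procedure) until 30 days after the date of partial nephrectomy", extended for drug-related toxicity until it falls to grade 1 or less.
- **Surgical events**: "Complications secondary to surgery delaying discharge will be considered an SAE".
- **Late related SAEs** (Reporting to Pfizer): SAEs that come to light at any time after the drug is stopped and are judged possibly related must be reported, but the drug named is pazopanib and the recipient GSK.
- **Participation-related SAEs**: collected and recorded from consent until the patient is off study.

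On the gap between drug and surgery, Section 4.1 says "Axitinib should be held for 1 day prior to surgery", and the note to the Section 5 calendar says "Nephrectomy will be performed ≥ 1 days after the last dose of Axitinib", with no maximum. Footnote 1 of the calendar places the End of Treatment/Withdrawal assessments at least 30 days after nephrectomy. Section 4.3 foresees radical as well as partial nephrectomy, and lists several reasons for stopping drug early.

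**The concern.** Two of the limits count from the last dose and one from surgery. Both dose-based limits sit beside a limb for events during the study, and nothing in the protocol says when the study, or being off study, ends for a patient. How long a site must report SAEs, and to whom, therefore depends on how that site reads an undefined term.

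This matters because safety and surgical morbidity are secondary objectives (Section 1). Section 2.4.2 lists hemorrhage, fistula formation and wound-healing complications among the actual or potential risks of axitinib, and these can appear after an operation. Two sites can both comply with Section 7 and still send different SAEs to the drug supplier and to the Study Chair.

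**Working it through.** The protocol states no figure to reproduce. The check is day arithmetic on its own limits, followed by a comparison of the clauses.

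**Inputs.** Pfizer tail: 5 days after last dose. Study Chair tail: 30 days after last dose. Toxicity follow-up: 30 days after surgery. Let g be the days from last dose to surgery. Section 5 requires g of at least 1. The 1-day hold in Section 4.1 gives g = 1 or 2, depending on how the held day is counted. g = 7 is my assumption, to show a longer gap.

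**Reading A: the study includes postoperative follow-up.** The limb for events during the study then covers the patient up to the calendar visit at least 30 days after nephrectomy. Days of the 30-day postoperative period outside either rule: 0.

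**Reading B: the study means the treatment period.** Only the dose-based tails remain after the last dose. The Pfizer tail ends on postoperative day 5 − g and the Study Chair tail on day 30 − g. Days beyond the tail = 30 minus the end day, to a maximum of 30.

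| g | Pfizer tail ends | Days beyond, of 30 | Study Chair tail ends | Days beyond, of 30 |
|---|---|---|---|---|
| 1 | 5 − 1 = day 4 | 26 | 30 − 1 = day 29 | 1 |
| 2 | 5 − 2 = day 3 | 27 | 30 − 2 = day 28 | 2 |
| 7 (assumed) | 5 − 7 = −2, before surgery | 30 | 30 − 7 = day 23 | 7 |

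**Patients who stop drug and have no surgery.** Footnote 1 of the calendar dates the withdrawal assessments from nephrectomy, so it gives these patients no end date. Once such a patient has left the study, the Study Chair is owed SAEs for 30 days after the last dose and Pfizer for 5. The difference is 30 − 5 = 25 days.

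**Do other clauses close the gap under Reading B?**

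- The clause on protocol-specific procedures or interventions has no day limit, but it requires causation. The protocol does not say whether nephrectomy counts, and Section 4.3 leaves the operation to the surgeon's discretion.
- The late related-SAE clause is open-ended, but read literally it applies to another drug and another company.
- The participation-related clause runs to off study, which is undefined. It speaks of collecting and recording, not of reporting to Pfizer.
- The toxicity follow-up sentence names partial nephrectomy only. A patient who has radical nephrectomy has no surgery-based end point in Section 7, although the calendar footnote covers nephrectomy in general.

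**The case against.** The strongest objection is that the rules work as they stand. Each is an either/or rule. A patient with toxicity follow-up under way and a protocol visit still to come is naturally in the study, so postoperative SAEs go to both recipients. The dose-based tails are not redundant on that reading, because they serve patients who leave without surgery. Different windows for different recipients are not in themselves a contradiction. Reporting to the FDA, reporting of unanticipated problems and reporting of Grade 4 toxicities carry no dose-based cut-off. Clavien complications and transfusions are study outcomes, and expedited SAE windows do not limit their collection.

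Most of this stands. A reader might infer that the windows run only from the last dose, so that most postoperative SAEs escape reporting. The text does not support that, because it drops the during-the-study limb from both rules. A reader might also apply the Section 2 rates for partial nephrectomy in large masses (20% major complications) to this trial and derive a number of missed SAEs. That does not hold either. The protocol says nothing about when those complications arise, the rates come from masses over 7 cm whereas eligibility here rests on RENAL score or hilar proximity, and the count would be zero on the natural reading.

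The objection does not supply an end to the study, a common tail for patients without surgery, a follow-up end point in Section 7 after radical nephrectomy, or a late-SAE duty that names the drug under study.

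**Conclusion.** The point holds as a defect of definition and alignment. On the natural reading, 0 of 30 postoperative days are lost to either recipient. On the narrower reading with a 1-day gap, 26 of 30 lie beyond the Pfizer tail and 1 of 30 beyond the Study Chair tail. The Study Chair shortfall is therefore trivial when surgery follows the last dose closely, and the exposure is mainly in reporting to Pfizer. It rests on a site treating the study as the treatment period, which the undefined term allows but does not favor, and on nephrectomy not counting as a protocol-specific intervention.

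Three parts do not depend on the narrower reading: the 25-day difference for patients who leave without surgery, the follow-up sentence limited to partial nephrectomy, and the late-SAE clause that names pazopanib and GSK. No number of missed SAEs can be derived from the document. The change is worth making because it is specific, bears on safety reporting and costs little.

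**What to change.** - Use one SAE window for Pfizer, the Study Chair and the Site PI, regardless of attribution: from consent to the later of 30 days after the last axitinib dose and 30 days after any nephrectomy, partial or radical. Let it replace the 5-day tail and the dose-only 30-day tail. This also gives patients without surgery a definite end date.
- Extend the toxicity follow-up sentence to any nephrectomy, and keep its existing extension for unresolved drug-related toxicity.
- Correct the late related-SAE clause to name axitinib and Pfizer.

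The cost is an amendment to the wording of Section 7 and a few more SAE forms. No new visits are needed for operated patients, since the calendar already places an assessment at least 30 days after nephrectomy.

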8. PHARMACEUTICAL INFORMATION

8.1 Description of Investigational Product

Axitinib

Axitinib is supplied as a series of aqueous film-coated tablets containing 5mg of agent

[figure not shown]
8.2 Physical and Chemical Properties of the Drug Substance

NDC Codes: 0069-0145-01, 0069-0151-11, 63539-026-01, 63539-044-01, 63539-044-02.

Approved Names: Inlyta

Chemical Name: N-methyl-2-[[3-[(E)-2-pyridin-2-ylethenyl]-1H-indazol-6-yl]sulfanyl]benzamide

Structural Formula:

Molecular Formula: C₂₂H₁₈N₄OS

Molecular Weight: 386.46952 g/mol

Physical Form: White to light yellow powder

Solubility: In aqueous media with a pH between 1.1 to 7.8, axitinib has a solubility of over 0.2 mg/mL.

Refer to the FDA label regarding the physical and chemical properties of axitinib and a list of excipients.

8.3 Dosage and Administration

Axitinib

Axitinib will be provided by Pfizer. For purposes of this study, Axitinib dosing will be defined by one 8 week cycle: Dosing will continue until prior to partial/radical nephrectomy, unacceptable toxicity, or withdrawal of consent .

Axitinib should be taken twice daily approximately 12 hr apart. May be taken with or without food. It may be swallowed whole with a glass of water; do not split, crush, or chew. If the patient vomits or misses a dose, an additional dose should not be taken; the next prescribed dose should be taken at the usual time

Specific recommendations regarding anticoagulants:

No interactions have been reported between axitinib and warfarin, aspirin, clopidogrel, ticagrelor, or rivaroxaban.

Specific recommendations regarding hypoglycemic medications including insulin:

Results from drug-drug interaction studies conducted in subjects with cancer suggest that there will be no clinically relevant pharmacokinetic interaction between axitinib and hypoglycemic agents. Decreases in serum glucose, however, have been reported in clinical studies with axitinib. Such changes may require an adjustment in the dose of hypoglycemic and/or insulin therapy. Subjects should be advised to report symptoms of hypoglycemia (e.g., confusion, visual disturbances, palpitations, sweating).

Overdose

There is no specific antidote for over dosage of axitinib, and treatment of overdose should consist of general supportive measures. Hemodialysis is not expected to enhance the elimination of axitinib, as axitinib is not significantly renally excreted.

9. MEASUREMENT OF EFFECT

9.1 Guidelines for Evaluation of Measurable Disease

All measurements should be taken and recorded in metric notation using calipers. All baseline evaluations should be performed as closely as possible to the beginning of treatment and never more than 6 weeks before the beginning of the treatment.

The same method of assessment and the same technique should be used to characterize each identified and reported lesion at baseline and during follow-up. Imaging-based evaluation is preferred to evaluation by clinical examination when both methods have been used to assess the antitumor effect of a treatment.

[figure not shown]
Conventional CT and MRI. These techniques should be performed with cuts of 10 mm or less in slice thickness contiguously. Spiral CT should be performed using a 5 mm contiguous reconstruction algorithm. This applies to tumors of the chest, abdomen, and pelvis. Head and neck tumors and those of extremities usually require specific protocols.

9.2 Response Criteria

Response to axitinib will be measured according to 3 mechanisms:

1. Percent in reduction of longest diameter of tumor.
2. RECIST criteria-Tumor response to therapy will be assessed by CT/MRI during second cycle of treatment according to the Response Evaluation Criteria in Solid Tumors (RECIST) version 1.1.1.²⁴ Clinical response of primary tumor will be classified by treating physicians as complete response (CR), partial response (PR), stable disease (SD), and progressive disease (PD), where:
 - a) Complete Response (CR): Disappearance of all target lesions
 - b) Partial Response (PR): At least a 30% decrease in the sum of the longest diameter (LD) of target lesions, taking as reference the baseline sum LD
 - c) Progressive Disease (PD): At least a 20% increase in the sum of the LD of target lesions, taking as reference the smallest sum LD recorded since the treatment started or the appearance of one or more new lesions
 - d) Stable Disease (SD): Neither sufficient shrinkage to qualify for PR nor sufficient increase to qualify for PD, taking as reference the smallest sum LD since the treatment started
3. RENAL score-morphometric measure which has been correlated with oncological prognosis, surgical risk stratification and renal functional outcomes in addition to response to primary TKI.²⁰

	1pt	2pts	3 pts
(R)adius (maximal diameter in cm)	≤4	>4 but < 7	≥ 7
(E)xophytic/endophytic properties	≥ 50%	<50%	Entirely endophytic
(N)earness of the tumor to the collecting system or sinus (mm)	≥7	>4 but <7	≤4
(A)nterior/Posterior	No points given. Mass assigned a descriptor of a, p, or x		
(L)ocation relative to the polar lines* * suffix "h" assigned if the tumor touches the main renal artery or vein	Entirely above the upper or below the lower polar line	Lesion crosses polar line	>50% of mass is across polar line (a) or mass crosses the axial renal midline (b) or mass is entirely between the polar lines (c)

[figure not shown]
For difficult to qualify/document cases, the primary surgeon may seek confirmation of the surgical Co-PIs ([name]/[name]) to confirm the change between baseline and post Rx status.

10. STATISTICAL CONSIDERATIONS

Sample Size/Power Calculation:

Our sample size calculation is based on the data of Rini et al. (2015) who reported that 80% (20/25) of patients successfully underwent partial nephrectomy; from our institutional database the success rate was utilizing Sunitinib the success rate in imperative indications was 78.6% (11/14).

Assuming a true rate of successful intervention of 75%, a one proportion z-test will have 80% power (Beta 20%) at the two-sided 0.05 (alpha) significance level to detect a rate of success of at least 56.4%. To account for a potential dropout rate of 10%, we will have total sample size to 50 (Figure)

Statistical Analysis:

We will examine patients in whom the operation was feasible vs. those in which it was not. Summary statistics (mean, standard deviation, quintiles, counts, and percentages) and plots will be produced for all demographic (i.e. age, sex, race, BMI, Charlson score, etc), clinical disease characteristics (tumor size prior to treatment, RENAL score), surgical outcomes (margin status, estimated blood loss, transfusions) and complications, and renal functional outcomes (change in eGFR, decline in GFR >50% of preoperative value, and dialysis dependence). In comparing any of these measures between patient groups, we will use either Fisher's Exact test or the Chi-Squared test for categorical variables and a t-test for continuous variables. We will consider the use of the Mann-Whitney U-test as a robust alternative if the assumptions of the t-test are not met.

We will use a logistic regression to examine the impact of factors associated with complications / blood transfusions and GFR decline > 50%, and a linear regression to examine factors associated with changes in GFR. Standard model diagnostics will be assessed before any inference is derived. All statistical analysis will be conducted using the latest version of R (R Foundation for Statistical Computing, Vienna, Austria. <http://www.r-project.org/>).

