Investigational Protocol

Proposed Title: “PADRES” (Prior Axitinib as a Determinant of Outcome of REnal Surgery)

Co-Principal Investigators: [name].¹
UCSD Moores Cancer Center
[name]
Mail Code: 0987
[name]
[contact]
[contact]
Email: [contact]

[name].
Cleveland Clinic Taussig Cancer Center
[name]
[name]
[contact]
[contact]
E-mail: [contact]

[name], PhD
Section of Urologic Oncology
Glickman Urological and Kidney Institute
[name]
[name]
[contact]
[contact]
[contact]

Co-Investigators:

[name]	(UCSD)
J. [name]	(UCSD)
[name]	(UCSD)
[name]	(UCSD)
[name]	(Cleveland Clinic)
[name]	(Cleveland Clinic)
[name], PhD	(Spectrum Health/Michigan State)
[name]	(Fox Chase Cancer Center)
[name]	(Netherlands Cancer Institute)
[name]	(MD Anderson)
[name]	(MD Anderson)
[name]	(UT Southwestern)
[name]	(Mayo Clinic)
[name]	(Mayo Clinic)

[name] (U Wisconsin)
[name] (NYU)
[name] (NYU)
[name] (Vanderbilt)
[name] (KU Leuven)
[name] (KU Leuven)

Statistician: [name], MS
Clinical and Translational Research Institute
UC San Diego Health
[name]
[name]
[contact]
Email: [contact]

Research Coordinator: [name], CCRC
Clinical Research Coordinator
UC San Diego Moores Cancer Center
Clinical Trials Office, Rm # 2011
[name]
[name]
[contact]
[contact]
[contact]
Email: [contact]

Responsible Data Manager: [name], MS
Database Program Manager
UC San Diego Health System-Department of Urology
[name]
Moores Cancer Center Office: 2032
[name]
[contact]
[contact]
Email: [contact]

Investigational Agent: Axitinib

Sponsor: University of California San Diego

Protocol Version Date: May 31, 2017

SCHEMA

A single arm phase II study of axitinib in patients with clear cell renal cell carcinoma (RCC) in patients with strong indications for partial nephrectomy (PN) for whom PN is not currently possible due to anatomic considerations and residual renal function concerns. Evaluation of tumor downsizing will be performed including changes of tumor complexity by nephrometry score (n=50 total).

Evaluation:

- 1) Cross Sectional Imaging (CT a/p, or MRI as indicated) to delineate renal mass and surrounding structures:

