1. OBJECTIVES

We hypothesize that pretreatment with axitinib will be safe and improve the feasibility of complex nephron sparing surgery in select patients with localized clear cell RCC and imperative indications for partial nephrectomy.

- 1 Primary objective: The primary objective of the study is to prospectively assess utility of axitinib in facilitation of partial nephrectomy where partial nephrectomy was not thought to be safe/possible in the setting of imperative indication for complex renal masses in renal cell cancer.**
- 2 Secondary objectives: To determine the safety, tumor diameter (per RECIST v1.1) volume change, surgical morbidity and renal functional outcomes following neoadjuvant axitinib for RCC.**

Anatomical/morphometric:

- a) tumor diameter/volume change,
- b) conversion of hilar to non-hilar tumors,
- c) reduction in RENAL morphometric score.

Functional Considerations:

- a) Requirement of acute dialysis
- b) Change in GFR
- c) Whether or not GFR crosses 30 threshold, or decline by GFR to >50% of baseline.

Safety indices:

- a) Incidence of Clavien >3 complications
- b) Avoidance of need for multiple blood transfusions

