2.3.2 Utilization of Primary Targeted Therapy Prior to Nephron Sparing Surgery

A potentially important and clinically promising indication for neoadjuvant targeted therapy is to downsize locally advanced and complex tumors and to enable nephron sparing

surgery when it may not have otherwise have been feasible, safe, or optimized.

Silberstein et al at UCSD reported on the efficacy of neoadjuvant TKI therapy prior nephron-sparing surgery in 12 patients with 14 tumors in the setting of locally advanced and/or metastatic disease and with imperative indication for nephron-sparing surgery; all patients had bulky local disease or central lesions. A mean tumor size reduction of 21.1% was observed, with a partial response in 4 of 14 (28.6%) tumors and stable disease in the remaining ten (71.4%) tumors. All attempted partial nephrectomies were successful with negative margins, and at a mean follow-up of 24 months, 10 of 12 patients are alive, with one dying from metastatic RCC. Three of the 14 renal units developed delayed urinary leaks which only occurred in those given postoperative sunitinib. These data provided proof of principle and suggested that in well selected patients with imperative indications for nephron-sparing surgery in the setting of locally advanced disease, primary TKI therapy results in tumor response and may facilitate or enable challenging partial nephrectomy.¹⁷ Rini et al. conducted a Phase II trial evaluating utility of pazopanib to optimize renal parenchymal preservation in patients with high complexity kidney masses (R.E.N.A.L. score 10-12) with perihilar tumors and in whom surgery was likely to otherwise yield a glomerular filtration rate of less than 30 ml/minute/1.73 m². A total of 25 patients were enrolled, with 71% of tumors demonstrating a decrease in R.E.N.A.L. score and 92% of patients experienced a reduction in tumor volume. Six of 13 patients for whom partial nephrectomy was not possible at baseline were able to undergo partial nephrectomy after treatment. Furthermore, mean parenchymal volume that could be saved with surgery increased from an estimated 107 to 173 cc (p = 0.0015).¹⁸

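### The 20/25 behind the 75% planning rate does not reconcile with 6/13 in Section 2.3.2, and no pre-treatment record of partial nephrectomy feasibility keeps already-feasible operations from counting as successes

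*Protocol*

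**What the plan says.** **Planning rate.** Section 10 names two sources. The first is the pazopanib phase II trial, which "reported that 80% (20/25) of patients successfully underwent partial nephrectomy". The second is institutional sunitinib data, in which "the success rate in imperative indications was 78.6% (11/14"). It then assumes a true rate of 75% and claims 80% power at two-sided 0.05 "to detect a rate of success of at least 56.4"%, with 50 patients in total after allowing for 10% dropout.

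**The same trial in the background.** Section 2.3.2 gives an enrolment of 25 and describes "patients with high complexity kidney masses (R.E.N.A.L. score 10-12) with perihilar tumors and in whom surgery was likely to otherwise yield" a GFR below 30. It then reports: "Six of 13 patients for whom partial nephrectomy was not possible at baseline were able to undergo partial nephrectomy after treatment".

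**Target population.** The Schema speaks of patients with "strong indications for partial nephrectomy (PN) for whom PN is not currently possible due to anatomic considerations" and residual renal function concerns. The primary objective in Section 1 is facilitation of PN "where partial nephrectomy was not thought to be safe/possible".

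**Eligibility.** Section 4 requires an imperative indication, a RENAL score of at least 10 or hilar proximity, and severe CKD as the expected result of radical nephrectomy. Exclusion 4 removes RENAL scores of 9 or less. No criterion asks whether PN itself is judged impossible or unsafe, and the Section 5 calendar has no such assessment. Section 9.2 mentions confirming a change from baseline, but only as an option in difficult cases.

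**The concern.** There are two linked problems.

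First, a figure on which the sample size is said to be based conflicts with the protocol's own account of the same study, so the planning rate cannot be checked.

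Second, the question is one of conversion: does axitinib make PN possible or safe where it was not? Section 4.3 describes failure in those terms. With no control arm, the patient's status before treatment is the only comparator. The surgical outcome listed in the Schema is ability to perform PN after therapy with negative margins, whatever was feasible beforehand. A PN that was already feasible and safe would satisfy it although axitinib changed nothing. The stopping rule in Section 11 counts the same operations, so it does not correct for this.

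**Working it through.** **1. The plan's own figure.** With 75% against 56.4%, two-sided 0.05 and n = 50, the arcsine method gives 79.8% power and a detectable rate of 56.35%. The usual one-proportion z-test gives 78.6%. The stated power therefore reproduces to within 2 points, and the question is about the input rate and the population.

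**2. Source counts, read as patients.**
- Enrolled 25, of whom 13 not possible at baseline; remainder 25 − 13 = 12.
- Highest possible number of PNs: 6 + 12 = 18, and 18/25 = 72%.
- To reach 20, the 12 others would have to supply 20 − 6 = 14 operations.

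**3. The second source.** 11/14 = 78.6%. If this is the sunitinib series in Section 2.3.2, then 14 counts tumours in 12 patients, and that section says "All attempted partial nephrectomies were successful with negative margins". The unit and the meaning of success are then both unclear.

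**4. How firm the rates are (exact 95% intervals).**

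| Count | Rate | Interval |
|---|---|---|
| 20/25 | 80% | 59% to 93% |
| 18/25 | 72% | 51% to 88% |
| 11/14 | 79% | 49% to 95% |
| 6/13 | 46% | 19% to 75% |

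**5. Effect of a lower planning rate, if 56.4% is the null.** The z-test is significant on the upper side from 32/45 or 36/50. At 32/45, z = (0.7111 − 0.564)/√(0.564 × 0.436/45) = 0.1471/0.0739 = 1.99. Exact binomial power:

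| True rate | 45 evaluable | 50 evaluable |
|---|---|---|
| 75% | 78% | 75% |
| 72% | 63% | 57% |
| 70% | 51% | 45% |

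**6. Do the entry criteria guarantee infeasibility?** In the cited trial, RENAL 10-12, perihilar tumour and a predicted GFR below 30 still left up to 12 of 25 outside the not-possible group. Some of those 12 may have been possible but unsafe, so the number who would fall outside this trial's target is unknown.

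**7. Effect of already-feasible operations (illustration).** The documents give no share f, so 10%, 20% and 30% are assumed, with every such operation succeeding, a true conversion rate of 56.4% in the rest, and 56.4% as the null. Overall rate = f + (1 − f) × 0.564.

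| f | Overall rate | P(significant), 45 | P(significant), 50 |
|---|---|---|---|
| 0 | 56.4% | 3% | 2% |
| 10% | 61% | 10% | 7% |
| 20% | 65% | 25% | 19% |
| 30% | 69% | 48% | 42% |

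**The case against.** **The anatomic criteria may be the definition.** Section 2.3.3 says that feasibility is assessed in complex masses identified by an objective morphometric measure, and exclusion 4 makes the anatomic criterion strict. Using RENAL complexity to stand for not safe or possible is a legitimate choice, and an unblinded surgeon's judgement is more open to bias. This stands as a reason to keep the criteria. It does not close the gap, because similar criteria in the cited trial did not single out the not-possible patients.

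**Baseline imaging is mandatory, so cases could be separated later.** Partly true: a masked review of baseline scans remains possible. It would be a reconstruction and would separate such cases only in part. The case report form is not available, so the gap is established only for the protocol text.

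**The 18/25 ceiling assumes patients as the unit.** Fair. Section 2.3.2 also counts tumours, and its 71% cannot come from 25 (17/25 = 68%, 18/25 = 72%). A different unit might explain 20/25, but Section 10 says patients and gives no other. Similarly, 3 of 14 renal units in the sunitinib series had urinary leaks, which would leave 11/14. That is inference, and the definition should be stated.

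**Stronger readings.** A reader might infer that the true rate is 46% and that the trial is bound to fail. The documents do not support this: 6/13 is small, concerns another drug, covers only the not-possible group, and has an interval reaching 75%. Nor do they show that 75% is wrong. It lies below both cited rates, and the interval for 18/25 includes it. A reader might also take the rise to 48% as the trial's actual error rate. It depends on assumed shares and on 56.4% being the null, and the documents do not show that even one already-feasible patient would be enrolled.

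**Conclusion.** The concern holds in a limited form and should be fixed. Read as patient counts, 20/25 is inconsistent with Section 2.3.2, which allows at most 18/25. The unit and success definition behind 11/14 are also missing. Neither rate is shown to describe patients in whom PN was not safe or possible. The Schema and objective set that population, but the protocol neither requires the judgement at entry nor shows a record of it. A success rate that mixes conversions with already-feasible operations would not cleanly answer the primary objective.

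The size is conditional. If the corrected rate were 72% and 56.4% is the null, exact power would be 63% with 45 evaluable or 57% with 50. The inflation from already-feasible operations is illustrative only. Invalidation of the primary result is not demonstrated. Which of 75% and 56.4% is the null is a separate question. The conflict in counts and the missing feasibility record do not depend on it.

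**What to change.** 1. **Reconcile Section 4 with the Schema and objective.** Keep the RENAL and hilar criteria. Before the first dose, have the surgeon record, against the baseline imaging, one of three categories: PN not possible; possible but not safe or not adequate for parenchymal preservation; feasible. Report the primary success rate in the first two groups together, with the all-enrolled rate and the not-possible rate alongside.
2. **Reconcile 20/25 and 11/14 with Section 2.3.2.** State the unit and the definition of success for each. If the corrected source rate is lower, restate the planning rate and the power.

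**Cost.** Protocol wording and one baseline form field. The judgement is subjective, which reporting the all-enrolled rate alongside helps to expose. The primary set may shrink by a number the documents do not give; if every enrolled patient falls in the first two groups, none is lost. The restated power may be less favourable than the present 80%.
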